## Proactive Prophylaxis With Azithromycin and Chloroquine in Hospitalised Patients With COVID-19 (ProPAC-COVID)

- Time to no oxygen supplement (or regular LTOT oxygen supplement)

In addition, several explorative endpoints.

Data is processed and analysed in SAS v.9.4 and graphs are generated in Microsoft Excel and SigmaPlot.

### 3.3.6. Sample size:

#### Randomised controlled study

Prerequisite: Type 1 error rate = 5%. Power = 80%. Two-sided statistics. Group sequential design with one scheduled interim analysis after randomisation of 113 patients (50% recruitment).

Analysis: T-test.

Sample size is calculated based on the following estimates and indicative figures:

Expected duration of hospitalisation with COVID-19: 10 days

SD for "Days alive and discharged within 14 days" in patients with lung disease and COVID-19: 4 days (up to 10 days hospitalization)

Estimated time for improvement/deterioration: 1.5 days.

This requires 226 patients randomised 1:1 with 113 in each group. This is a fixed sample size. It is assumed that most patients complete the intervention.

However, for interim analysis, the Data and Safety Monitoring Board (DSMB) may recommend the steering committee to expand sample size.

### 3.3.7 GCP Monitoring:

Frequency and depth are determined by the GCP units. Initiation visits and the first monitoring visits to all centres will be conducted off-site, i.e. without a physical meeting, due to the SARS-CoV-2 pandemic. Consent sheets will be scanned into an online system (REDCap or journal system) that can be accessed by GCP monitors.

## **4. Interim Analysis and Data and Safety Monitoring Board**

After recruiting half the sample size (approximately 113 patients), an interim analysis will be performed focusing on safety. An external Data and Safety Monitoring Board is appointed.

The interim analysis will be prepared and presented by physician [name]. The groups will be presented as "Group A" and "Group B" and DSMB will only be unblinded if they ask the steering committee for the study on this.

## **5. Blood samples:**

As part of usual care, blood samples are taken daily from the time of inclusion and as long as the patient is admitted. Blood samples include haemoglobin (Hb), leukocytes + differential count, thrombocytes, C-reactive protein (CRP), Na+, K+, albumin, creatinine, urea, amylase, alkaline phosphatase, beta-2-Microglobulin, fibrinogen, glucose, TSH, D-dimer, APTT, calcium, triglycerides, ferritin, bilirubin, ALAT, INR, and lactate dehydrogenase (LDH), see Table 1. These blood samples are analysed at the hospitals.

In addition, supplemental blood tests and material obtained with nasal swabs will be performed according to the sub-study protocols. Material from this will be included in a research biobank for the trial, and after completion of the trial in another regional biobank. The trial is expected to end in February 2021, and the material will then be transferred to the regional biobank.

For the present trial, the results of blood tests are collected from the patient record.

## **6. Side effects, risks and disadvantages:**

The treating physician may at any time discontinue intervention with IMP if, in clinical and/or paraclinical assessment, it is deemed contraindicated.

### Blood tests:

Serious side effects to regular blood sampling (venous puncture) are rare. Frequent (5-15%) can be seen transient discoloration of skin around the insertion site.

### X-ray:

Chest X-rays correspond to a radiation dose of approx. 0.1 millisievert (mSv). This should be compared with the average background radiation in Denmark of approx. 3 mSv per year. There are no documented adverse effects of the radiation dose received by Chest X-rays in the literature. Therefore, we believe that the study is not associated with any risks or side effects.

### Side effects of the trial medicine:

See [www.medicin.dk](http://www.medicin.dk)

### Azithromycin:

Very common (>10%) Abdominal pain, Diarrhoea, Flatulence, Nausea.

## Proactive Prophylaxis With Azithromycin and Chloroquine in Hospitalised Patients With COVID-19 (ProPAC-COVID)

Common (1-10%) Powerlessness, Decreased appetite. Vomiting, Taste Disorders. Decreased lymphocyte count. Decreased serum bicarbonate. Arthralgia. Headaches, Paraesthesia, Dizziness. Skin itching, rash. Visual disturbances.

Uncommon (0.1-1%) Pain. Hepatitis, Oral candidiasis. Dyspnea, Pneumonia, Oedema. Eosinophilia, Leukopenia, Neutropenia. Elevated serum bicarbonate, Hyperchloremia, Hyperglycaemia, Hyperkalaemia, Hyponatremia, Hypokalaemia, Hyponatraemia. Arthritis, Back Pain. Nervousness, Somnolence. Facial oedema, Dermatitis, Photosensitivity. Candidiasis, Infections. Metrorrhagia, Kidney Pain, Testicular Disease, Vaginitis. Hearing loss, Tinnitus.

Rare (0.01-0.1%) Cholestasis, Liver Impact. Agitation. Acute generalized exanthematous pustulosis\*, Allergic reactions\*, Angioedema\*, Hypersensitivity.

Not known Fulminant hepatitis, Hepatotoxicity, Hepatic insufficiency, Pancreatitis, Pseudomembranous colitis. Arrhythmias, Extended QT interval, Hypotension, Torsades de pointes tachycardia. Haemolytic anaemia, Thrombocytopenia. Aggravated myasthenia gravis. Aggressiveness, Anxiety, Delirium, Hallucinations, Hyperactivity, Hypesthesia, Seizures, Syncope. DRESS - drug reaction with eosinophilia and systemic symptoms, Erythema multiforme, Stevens-Johnson syndrome, Toxic epidermal necrolysis. Anaphylactic reaction. Acute renal failure, Interstitial nephritis.

\*In case of allergic reactions, including acute generalized exanthematous pustulosis and DRESS, azithromycin should be discontinued.

### Hydroxychloroquine:

Very common (> 10%) Abdominal pain, Nausea.

Common (1-10%) Eating refusals. Diarrhoea, Vomiting. Emotional lability, Headaches. Skin itching, rash. Accommodation difficulty.

Uncommon (0.1-1%) Liver effect. Nervousness, Sensomotor disorders, Dizziness. Alopecia. Corneal oedema, Double vision, Retinopathy \*, Tinnitus.

Not known Fulminant liver failure. Bronchospasm, prolonged QT interval\*\*, Cardiomyopathy. Aplastic Anaemia, Bone Marrow Depression, Influence of the Blood Image (agranulocytosis, anaemia, leukocytopenia, thrombocytopenia). Aggravation of Porphyria, Hypoglycaemia. Myopathy. Extrapyramidal genes, Cramps, Neuropathy, Palsy, Psychosis, Suicidal behaviour. Acute generalized exanthematous pustulosis\*\*\*, Exfoliative dermatitis, Erythema multiforme, Photosensitivity, Stevens-Johnson syndrome, Toxic epidermal necrolysis. Allergic reactions (including DRESS syndrome), Angioedema. Hearing loss, Macular and retinal degeneration, Maculopathy.

\*Retinopathy:

## Proactive Prophylaxis With Azithromycin and Chloroquine in Hospitalised Patients With COVID-19 (ProPAC-COVID)

- With pigment change requires careful dosing and careful control. When using rheumatologic doses, eye examination by an ophthalmologist is recommended before starting treatment and with follow-up to check for any eye manifestations that may arise. Annual monitoring after 5 years of treatment is recommended, however in risk patients initially annual control, see also Chloroquine derivatives (inflammatory rheumatic diseases), side effects.
- With cardiomyopathy can be fatal.
- With macular degeneration is seen and may be irreversible.
- With reversible corneal changes with oedema and blemishes can cause blurred vision or photophobia.
- With blurred vision accommodation is dose-dependent and reversible.
- In malaria treatment and prophylaxis, fewer and milder side effects occur.

\*\*Prolonged QT interval has been seen in patients with particular risk factors for it.

\*\*\*Acute generalized exanthematous pustulosis must be distinguished from psoriasis. Psoriasis exacerbation may occur. May be associated with fever and hyperleukocytosis.

An adverse reaction (AR) is defined as any adverse and undesirable reaction to a trial drug regardless of dose. An adverse event (AE) is defined as any adverse event in a patient or subject in a clinical trial following treatment with a drug, without necessarily linking this treatment to the adverse event.

Since the trial drugs are well known and have been used for many years, we will only record side effects not mentioned in the respective drug summary of the trial drug.

A severe adverse reaction or event (SAR/SAE) is defined as an event or adverse event that, regardless of dose, results in death, is life-threatening, results in hospitalization or prolongs hospitalization, results in significant or persistent disability or incapacity, or leading to a congenital anomaly or malformation.

Investigators must immediately (= within 24 hours) report serious incidents and serious adverse reactions (SAEs and SARs) to the sponsor regardless of whether they are described in the respective product summary. This allows the sponsor to assess the benefits and risks along the way in the study.

Events and adverse events recorded during the period from the patient have received the first dose of trial medication up to and including day 15.

Recording and reporting of all events and adverse events will end when the trial drug is stopped.

A high degree of comorbidity and death is seen in this patient group and therefore it is also expected that prolonged admissions, re-admissions, NIV, Respirator treatment and death will occur in this patient group. Therefore, these parameters will not be considered as a SAE.

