### 3.3.3. Data collection, surveys and follow-up:

The primary daily project management is carried out by the project manager. In addition, a project group (investigators), consisting of doctors from the departments involved, is trained to assist the project manager with the recruitment, sampling and follow-up of patients. All medical decisions regarding patients will be taken by a physician. Data is collected in Case Report Forms (CRF) for each individual patient.

Prior to consent to participate in the trial, we will only assess the specific information needed to assess inclusion and exclusion criteria. No other information will be accessed.

It is the attending physician who asks if patients are interested in hearing more about the trial. If yes, an investigator is contacted, who will inform the patient about the trial.

As part of the study, all patients will be regularly monitored for oxygen saturation, heart rate, blood pressure, respiratory rate and temperature during hospitalisation.

The following information will also be obtained:

- Date of birth, age and gender
- Height, weight and BMI
- Use of medicine
- For patients with chronic obstructive pulmonary disease (COPD) classification in GOLD 1-4 and GOLD A-D (symptoms assessed via MRC degree)
- Systematic screening for co-morbidities
- Smoking history with pack years, current smoking status and alcohol consumption
- Information from the chest x-ray
- Arterial-blood gas analysis (pH, pCO2, pO2, Base Excess, oxygen supplementation)
- Hb, leucocytes + differential count, CRP, kidney function, liver parameters, electrolytes, LDH
- ECG, vital status, and adverse events

And from the patients' medical journal:

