#### Azithromycin:

Day 1-3: 500 mg x 1

Day 4-15: 250 mg x 1

If the patient is unable to take the medication orally by themselves, the medication will, if possible, be administered by either stomach-probe, or alternatively, temporary be changed to clarithromycin 500 mg x 2 (this only in agreement with either study coordinator [name] or principal investigator [name]). This will also be done in the control group if necessary. The patient will switch back to azithromycin when possible.

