#### Hydroxychloroquine:

Furthermore, the patient will be treated with hydroxychloroquine as follows:

Day 1-15: 200 mg x 2

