## Proactive Prophylaxis With Azithromycin and Chloroquine in Hospitalised Patients With COVID-19 (ProPAC-COVID)

Follow-up is done on days 14, 29, 90 and 365 days, by accessing the electronic medical record system. The specific information obtained, and its purpose can be found in section 3.3.3.

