### Regarding other treatment with antibiotics:

If antibiotic therapy is deemed indicated to the patient due to e.g. pneumonia or if it becomes standard therapy, piperacillin-tazobactam should be given as an empirical treatment at a dose adjusted to renal function. In case of penicillin allergy, cefuroxime is also given at a dose appropriate to renal function, weight and age. When positive microbiology is available, immediately switch to targeted treatment.

If *specific suspicion of atypical pneumonia* is raised, ciprofloxacin is administered at a dose of corresponding to kidney function and concomitant examination for atypical pneumonia will be performed. If negative, ciprofloxacin is discontinued. If positive, ciprofloxacin treatment is continued for the duration of treatment corresponding to the microorganism detected. If there is a specific need for treatment with macrolide and where other options are not available (e.g. allergy to fluoroquinolones, or when there is an estimated need for combination treatment of e.g. legionella pneumonia), consult with an investigator, and in this case it may be decided to discontinue azithromycin (active) or azithromycin placebo. In this case, treatment stops without unblinding.

Furthermore, ECG recordings during the treatment period will be analysed with focus on QTc. At QTc (F) > 480/470 ms for respectively women and men, IMP will be discontinued for safety reasons (but the patient remains in the study).

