#### Secondary endpoints:

## Proactive Prophylaxis With Azithromycin and Chloroquine in Hospitalised Patients With COVID-19 (ProPAC-COVID)

Secondary endpoint no. 1:

Ordinate outcome. The patient is categorized into one of the following 8 categories on day 15:

1. Dead
2. Hospitalised and mechanical ventilation or ExtraCorporalMembraneOxygenation (ECMO)
3. Hospitalised and Non-invasive ventilation or high-flow oxygen device
4. Hospitalised and given oxygen supplements that do not live up to oxygen supplements in (2) or (3) - e.g. oxygen on nasal catheter
5. Hospitalised and do not receive oxygen supplementation but need treatment (COVID-19 related or other)
6. Hospitalised and do not receive oxygen supplements and do not need treatment (just observed)
7. Discharged with restriction on activities, may be free of oxygen depletion or use LTOT ("home oxygen")
8. Discharged, no restrictions on activities

Other secondary endpoints:

- Admitted to the intensive care unit in the two groups (0 vs. 1) during the index admission
  - o For patients admitted to intensive care unit: number of days on intensive care (Length of stay, ICU)
- Have been on Non-Invasive Ventilation (NIV) (0 vs. 1) during index hospitalisation
- Dead at day 30
- Duration (days) of index hospital admission
- Days alive and discharged from hospital within 30 days (summarises both whether the patient is alive and discharged from hospital)
- Dead at day 90 (reported later)
- Dead within 12 months (reported later)
- Number of readmissions for all causes within 30 days
- Number of days on NIV or mechanical ventilation during index admission
- Delta PaO2 day 1 (baseline) to day 4 (72 hours). At the same time oxygen supplements and oxygen systems are registered
- Delta PaCO2 day 1 (baseline) to day 4 (72 hours)
- pH day 4 (72 hours)

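### For a patient who completes the course, adverse event recording ends on the day of the last dose (day 15), so a serious reaction starting later is not recorded or assessed as one

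*Protocol*

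**What the plan says.** Dosing (Protocol 3.3.4): azithromycin ends with "Day 4-15: 250 mg x 1" and hydroxychloroquine is given "Day 1-15: 200 mg x 2". The SAP introduction repeats both schedules.

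End of safety recording (Protocol section 6): two sentences set it. One fixes the period as running from "the first dose of trial medication up to and including day 15". The other ties it to treatment: "Recording and reporting of all events and adverse events will end when the trial drug is stopped". The same section asks for SAEs and SARs to reach the sponsor within 24 hours. It also states that prolonged admission, re-admission, NIV, respirator treatment and death will not count as SAEs, because they are expected in this population.

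Record reviews (end of Protocol 3.3.4): "Follow-up is done on days 14, 29, 90 and 365 days, by accessing the electronic medical record system". For what is collected, that passage refers to section 3.3.3, which lists "ECG, vital status, and adverse events" without attaching a day.

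Outcomes beyond day 15 (Protocol 3.3.5): the secondary endpoints include death at day 30, days alive and discharged within 30 days, and "Number of readmissions for all causes within 30 days". Under its arrhythmia heading, the SAP counts patients with QTc(F) above 500 ms at any point after baseline, and ventricular arrhythmias. It gives no end day for either.

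**The concern.** Safety recording normally runs some way past the last dose, because a reaction to the final doses need not appear on the day they are taken. Here the end of recording and the end of dosing coincide. The protocol's own side-effect lists include serious reactions such as torsades de pointes, fulminant hepatitis, pseudomembranous colitis, DRESS and toxic epidermal necrolysis. If one of these began on day 16, nothing in the plan would require anyone to look for it, record it as a reaction or judge its relation to trial drug. Patients discharged during the course take their capsules at home with a diary, so staff may not see a late reaction at first hand.

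The gap is avoidable. The investigators will open the same records again on day 29 and already need information on death and readmission from that period. What is at stake is the completeness of the serious-reaction data, in a trial that combines two drugs for which the protocol itself lists QT prolongation.

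**Working it through.** The plan gives no figure for a post-treatment safety window, so there is none to reproduce. The check is a count of days and a comparison of passages.

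**Inputs**
- Last planned dose of each drug: day 15 (Protocol 3.3.4).
- End of event recording, fixed-day sentence: day 15 inclusive (Protocol section 6).
- End of event recording, treatment-linked sentence: the day trial drug stops (Protocol section 6).
- Record reviews: days 14, 29, 90 and 365 (Protocol 3.3.4).

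**Step 1: a patient who completes the course**
- Post-dose window = last day of recording − last dosing day = 15 − 15 = 0 days. Both sentences give this answer.
- The day-14 review falls before the last dose, so day 29 is the first review after treatment ends.
- Window if recording ran to that review = 29 − 15 = 14 days (days 16 to 29).

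**Step 2: a patient who stops early**

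The two sentences no longer agree here. Stop days 3, 5 and 8 are assumed for illustration only.

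| Last dose on day | Fixed-day sentence (15 − stop) | Treatment-linked sentence | Recording to day 29 (29 − stop) |
|---|---|---|---|
| 3 | 12 | 0 | 26 |
| 5 | 10 | 0 | 24 |
| 8 | 7 | 0 | 21 |
| 15 | 0 | 0 | 14 |

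The conflict affects real cases. When QTc passes the protocol's limit, "IMP will be discontinued for safety reasons (but the patient remains in the study". Under the treatment-linked sentence, event recording for that patient closes at the stop.

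**Step 3: what is still seen after day 15**
- *Death and readmission to day 30* are counted as secondary endpoints. Section 6 removes both from the SAE definition. A readmission on day 17 for drug-induced hepatitis would therefore enter the count without any required cause or causality judgement.
- *QTc above 500 ms and ventricular arrhythmias* are SAP analysis items with no end day. They do not themselves order collection after day 15, and the footnotes to the Protocol 3.3.3 schedule link the follow-up ECG to remaining days of admission. Liver, skin and bowel reactions are outside them.
- *SUSAR reporting* (7 and 15 days) runs from the sponsor's awareness and has no end date. A late event that happened to reach the sponsor could still be reported, but nothing requires a search for one.
- *The adverse events item in Protocol 3.3.3* carries no day in the visible text, so it does not displace the two explicit stops in section 6.

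**Step 4: would changing one sentence be enough?**

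No. If the fixed-day sentence were moved to day 29 and the other left alone, recording for a completer would still end on day 15 under the treatment-linked sentence. The two sentences would then conflict for every patient, not only for those who stop early.

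**Step 5: reporting delay under a day-29 search**

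An event with onset on day 16 that is first found at the review is 29 − 16 = 13 days old. The 24-hour rule therefore needs a stated starting point.

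**The case against.** The strongest reply is that the plan is not blind after day 15. Deaths are followed to day 30, day 90 and 12 months, all-cause readmissions to day 30, and the SAP's arrhythmia items have no closing date. The primary endpoint covers 14 days, so event recording to day 15 already spans the primary window. Section 3.3.3 names adverse events among the data to be obtained, and the day-29 review refers back to that section. The schedule table is not visible in the text available, so part of what is collected on day 29 cannot be checked.

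Much of this stands, and it limits the point. A reader might infer that serious harm after day 15 goes wholly unseen. The documents do not support that: the gravest consequences are counted, though as outcomes without an attributed cause. What is lost is their recording and assessment as SAEs or SARs. The undated item in section 3.3.3 does not cancel two explicit stops, but it is a reason to reconcile the passages.

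A reader might also infer that the gap pushes the safety comparison towards no difference between arms. That would need an excess of drug-caused serious events after day 15. The documents give no late-event rate, onset time or half-life, and the same rule applies to both blinded arms. Incomplete ascertainment is shown. A direction of bias is not.

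**Conclusion.** The point holds in a limited form. A completer has 0 days of adverse event recording after the last dose, against the 14 days that an already planned record review could supply. A serious reaction with onset on day 16 or later is not recorded as an SAE/SAR or assessed for causality. A resulting death or readmission by day 30 appears only as an endpoint count, and the SAP's arrhythmia items cover only two kinds of event.

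The number of events missed and any direction of bias cannot be determined from the documents. The conclusion assumes that the two stop sentences in section 6 mean what they say and that the unseen schedule table does not extend them. For patients who stop early, the same sentences contradict each other, so a single correction should settle both matters. This is a worthwhile and cheap improvement to safety ascertainment. It does not affect the primary analysis.

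**What to change.** 1. **Protocol section 6, both sentences together.** State one SAE/SAR recording window for all patients, whether or not drug was stopped early, from first dose up to and including the day-29 record review. Recording of non-serious events can end at day 15. Remove or reword the sentence that ends all recording when trial drug stops, since it would otherwise cancel the change.
2. **Reporting clock.** State that the 24 hours run from the investigator's awareness of the event.
3. **Readmissions and deaths after day 15.** Record the cause and any suspected relation to trial drug, so that excluding these events from the SAE definition does not hide a drug reaction.
4. **Protocol 3.3.3.** Attach the same window to the adverse events item.
5. **SAP.** Add a table of SAEs/SARs by arm for days 1–15 and days 16–29.

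The cost is protocol and SAP wording, plus a modest increase in SAE listing and causality assessment at a review already scheduled. No visit or test is added. The drawback is delay: an event found only at the day-29 review may be reported up to about two weeks after onset.

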## Proactive Prophylaxis With Azithromycin and Chloroquine in Hospitalised Patients With COVID-19 (ProPAC-COVID)

- Neurogenic hearing loss
- Psoriasis
- Retinopathy
- Maculopathy
- Visual field changes
- Breastfeeding
- Severe liver diseases other than amoebiasis (spontaneous INR > 1.5)
- Severe gastrointestinal, neurological and hematological disorders (investigator-assessed)
- eGFR <45 ml/min/1.73 m^2
- Clinically significant cardiac conduction disorders/arrhythmias or prolonged QTc interval (QTc (f) of > 480/470 ms).
- Myasthenia gravis
- Treatment with digoxin\*
- Glucose-6-phosphate dehydrogenase deficiency
- Porphyria
- Hypoglycaemia (Blood glucose at any time since hospitalization of <3.0 mmol/L)
- Severe mental illness which significantly impedes cooperation
- Severe linguistic problems that significantly hinder cooperation
- Treatment with ergot alkaloids

\*The patient must not be treated with digoxin for the duration of the intervention. For atrial fibrillation/flutter, select according to the Cardiovascular National Treatment Guide (NBV): Calcium antagonist, Beta blocker, direct current (DC) conversion or amiodarone. In case of urgent need for digoxin treatment (contraindication for the aforementioned equal alternatives), the test drug should be paused, and ECG should be recorded daily.

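### Protocol section 6 gives two end dates for recording adverse events, and read literally they differ for patients who stop trial drug early

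*Protocol*

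**What the plan says.** Protocol section 6 (side effects, risks and disadvantages) sets the recording period as running "from the patient have received the first dose of trial medication up to and including day 15". The next sentence reads "Recording and reporting of all events and adverse events will end when the trial drug is stopped". Nothing links the two or says which prevails.

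Section 3.3.4 schedules both drugs to the same last day: azithromycin "Day 4-15: 250 mg x 1" and hydroxychloroquine "Day 1-15: 200 mg x 2".

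The protocol foresees early stops in three places:

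- Section 3.3.4, under other antibiotic treatment, for a QTc finding: "IMP will be discontinued for safety reasons (but the patient remains in the study".
- The same subsection, where a macrolide is specifically needed: "in this case it may be decided to discontinue azithromycin (active) or azithromycin placebo". This concerns one of the two drugs only.
- Section 6: "The treating physician may at any time discontinue intervention with IMP if, in clinical and/or paraclinical assessment, it is deemed contraindicated".

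Section 6 also sets what is recorded. Side effects are recorded only if the product summary does not list them. Serious events and serious reactions go to the sponsor within 24 hours whether listed or not. Prolonged admission, readmission, NIV, respirator treatment and death do not count as SAEs.

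The SAP text sets no adverse-event window and plans no AE or SAE comparison between arms. Its safety items are mortality and, under Arrhythmias, post-baseline QTc(F) above 500 ms and ventricular arrhythmias. Its adherence section counts completion of each drug separately.

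**The concern.** One sentence fixes a calendar end and the other ties the end to treatment. A site with a patient taken off drug on, say, day 6 cannot tell from section 6 whether to go on recording to day 15. Sites could follow different rules.

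If the second sentence is followed as written, capture ends in patients whose drug may have been stopped for a suspected reaction, which is when later or evolving events are of interest. Section 6 lists QT prolongation for both active drugs and section 3.3.4 makes QTc a reason to stop, so stops could be more frequent in the active arm. Event observation time would then be shorter in that arm, and the event counts in the end-of-trial safety report would not be like for like. That fits poorly with the SAP's intention-to-treat principle, under which patients are analysed as allocated whatever treatment they received.

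**Working it through.** The protocol states no figure to reproduce. The check sets the two rules side by side and measures the distance between their end dates.

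**Inputs.** Fixed rule: recording ends on day 15 (section 6). Treatment-linked rule: recording ends on the stop day d (section 6, next sentence). Planned last dosing day: 15 for both drugs (section 3.3.4). Distribution of d: not given. Section 3.3.6 says only that most patients are assumed to complete.

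**Step 1: difference in end dates.** Gap = 15 − d days. The stop days between the two extremes are assumed, for illustration only.

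| Stop day d | Gap 15 − d (days) | Share of the 15-day window |
|---|---|---|
| 1 | 14 | 14/15 = 93% |
| 4 | 11 | 11/15 = 73% |
| 8 | 7 | 7/15 = 47% |
| 12 | 3 | 3/15 = 20% |
| 15 (completer) | 0 | 0% |

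The rules coincide for a completer and separate for anyone who stops sooner.

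**Step 2: do the affected patients exist in the plan?** Yes. The QTc stop expressly keeps the patient in the study. The physician's stop in section 6 concerns the drug and does not say that the patient leaves the study.

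**Step 3: one drug or two.** The treatment-linked sentence speaks of the trial drug in the singular, but there are two. Suppose azithromycin or its placebo stops on day d and hydroxychloroquine or its placebo continues to day 15. If the first stop counts, recording ends on day d while the patient is still taking study medication. If the last stop counts, it ends on day 15. The sentence does not choose between them, and the two readings are again 15 − d days apart.

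**Step 4: what falls in the gap.**

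| Item | Affected by the choice of rule? |
|---|---|
| Event that prompted the stop | No, it precedes the stop |
| Listed non-serious side effects | No, not recorded under either rule |
| Death, NIV, respirator treatment, prolonged admission, readmission as SAEs | No, exempt under either rule |
| Other SAEs/SARs arising after the stop, up to day 15 | Yes |
| Unlisted side effects arising after the stop, up to day 15 | Yes |
| Mortality endpoints; SAP QTc and arrhythmia counts | Not stated to end at drug stop |

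**The case against.** The strongest reply is that the sentences state one rule twice: record to day 15, then cease because treatment has ended. They are adjacent and the dosing schedule ends that day, so this is plausible. It is not proven. The second sentence does not refer to the planned end and would then add nothing to the first, and section 3.3.4 itself speaks of treatment stopping when azithromycin is discontinued early. This reply does rule out calling the text a contradiction for all patients.

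A second reply is that the earlier of the two dates applies. The fixed-window sentence has no such qualifier, and this reading would confirm the loss of events after an early stop.

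A third is that the assessment table may settle the matter. Section 3.3.3 lists adverse events among the data obtained, but the table itself is not in the text available for this review. It should be checked first. Even if it is clear, the two sentences still need to be aligned with it.

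A fourth is that the consequence is small. Much of this stands: Step 4 shows how narrow the affected class is, the SAP plans no AE/SAE comparison that unequal follow-up would distort, and most patients are assumed to complete.

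A reader might go further and infer that a pause also ends recording, because the digoxin footnote in section 3.3 says "the test drug should be paused, and ECG should be recorded daily". The documents do not support that: the protocol uses pausing and discontinuing as different terms. Nor do they support inferring that the reaction leading to a stop is lost, or that the efficacy endpoints are affected.

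**Conclusion.** The point holds as an ambiguity in a safety-recording rule. Read literally, the two sentences in section 6 give end dates 15 − d days apart for a patient who stops on day d, from 0 for a completer to 14 at most. No available passage says which governs or whether stopping one drug is enough. What could be lost is limited to SAEs/SARs and unlisted side effects arising after an early stop and by day 15.

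This rests on taking a stop to include early discontinuation, and on the missing assessment table not resolving it. A difference in observation time between arms is possible, because QT prolongation is a listed effect of both active drugs, but it is not shown: the documents give no stop rate, so no arm-level size is claimed. Nothing follows for sample size, type I error or the primary estimate. The clinical stopping rules are not questioned. The wording should be corrected, because the text as it stands permits safety recording to end at a safety stop and the correction is cheap.

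**What to change.** Replace the two sentences in section 6 with one that sets a single fixed window for recording and reporting AEs and SAEs in every patient who received at least one dose, whether or not one or both drugs were stopped early. The existing window to day 15 would serve. For example: *For every patient who has received at least one dose, adverse events and SAEs are recorded and reported from that dose through day 15, including after early discontinuation of either or both trial drugs.* Bring the assessment table into line if it says otherwise.

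If the planned end was always meant, this changes nothing in practice. Otherwise the cost is some extra event recording after early stops. Capture after discharge may be incomplete, because follow-up in section 3.3.4 is by medical record: the day-14 review falls one day before the window closes and the next is on day 29. The adherence phone call described with the trial medication, whose timing is not stated, could carry an adverse-event question.
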